Primary objective	To determine treatment effect on caregiver burden measured as Resource Utilization Dementia (RUD), and the Relative Stress Scale (RSS). Based on the correlation coefficient, we will use all three subcategories of RUD separately. Total score will be used when assessing RSS. Further, we will evaluate the economic consequences of the treatment by calculating Incremental Cost-Effectiveness Ratio (ICER) and quality adjusted life years (QALY).
Secondary objectives	To determine treatment effect on quality of life (QoL) using the European Quality of Life – 5 dimension – 5 levels (EQ-5D-5L), EQ-5D-VAS scale, Quality of Life in Alzheimer's disease scale (QoL-AD); neuropsychiatric symptoms in dementia using the Neuropsychiatric Inventory 12 item (NPI-12), agitation in dementia using Cohen-Mansfield Agitation Inventory (CMAI), depression in old age (Geriatric Depression Scale - GDS), functional level for instrumental and personal activities (ADL and IADL), and the caregiver rating of clinical meaningful change using Clinical Global Impression of Change (CGIC).
Exploratory objectives	
In line with total score of RSS, we will also explore the treatment effect on both single and clustered items.
 
In line with total score of QoL based instruments (EQ-5D-5L, QoL-AD, QoL – CG, GDS), we will also explore the treatment effect on both single and clustered items
 
To assess the effect on pain in dementia using the Mobilization – Observation – Behavior – Intensity Dementia Pain Scale (MOBID-2)
 
To determine the characteristics of the dyads who had the highest improvement in RUD and RSS, i.e., those who benefitted the most from the intervention.

Endpoints	
Primary endpoint: Change in caregiver burden and informal care time among the caregivers in the intervention group during active intervention period, and the follow-up. Change in Cost-efficiency of treatment.
 
Secondary endpoint: Improvement in QoL for both PwD and caregivers. Reduction in neuropsychiatric symptoms in dementia and functional level during active intervention period and follow-up.
 
Exploratory endpoint: Reduction in pain during active intervention period.

Treatments	Allocation to municipal coordinator delivering the multicomponent LIVE intervention (L:learning, I: innovation, V: volunteering and E:empowerment) or care as usual.
Number of patients	315 dyads will be screened to achieve at least 105 dyads per municipality.

Safety analysis	Not applicable

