Efficacy: primary	x		
Efficacy: secondary	x		x
Efficacy: other	x	x	x

General Statistical Methods and Definitions

General statistical methods

The statistical analysis will be presented by treatment group for the different analysis sets as outlined in section 4.

Stepped wedge design (SWD) do not strictly feature a treatment and control group, and thus, the summary statistics will include all participants at baseline, and the characteristics according to intervention sequences.

Continuous variables will be summarized using descriptive statistics (means and interquartile ranges), and categorical variables will be presented by frequencies and percentages. A table will present the number of caregivers and PwD with the following data: missing values, mean, median, standard deviation and confidence intervals.

Means and median as well as percentages will be presented with 1 additional decimal place and standard deviation by 2 additional decimals.

If the number of PwD or caregivers in a category is 0, then percentage will not be displayed.

P-values will be reported to 3 decimal places.

Unless otherwise specified, all statistical tests will be two-sided.

Causal model

Due to the longitudinal structure of the collected trial data, we considered the following linear mixed model to estimate and identify the treatment effect due to the intervention. Our SWD, consisting of $j = 3$ municipalities and 3 steps, is a closed cohort design, and thus, time related confounders are important to adjust for [5] when assessing treatment effect.

Mixed-effects regression is one of the most common approaches when estimating the intervention effect in SWD [6, 7]. In our design, we will consider the following model as our primary analysis model, assuming a constant treatment effect.

$$(1) Y_{ijt} = \beta_0 + O_{ijt}\beta_1 + X_{ijt}\beta_2 + b_i + \epsilon_{ijt}$$

where notation Y_{ijt} refers to the primary outcome caregiver burden (RUD and RSS), elaborated in section 3 Study Design, for individual i nested in municipality j at time point t . O_{ijt} is the treatment indicator (effect of receiving assistance from a municipality coordinator) and β_1 is the average treatment effect parameter of interest. Since the study collects repeated observations from the same participants, we consider a longitudinal regression model that adjusts for participant-level random effect, $b_i \sim N(0, \sigma_b^2)$, which corresponds to a compound symmetric correlation structure.

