$\epsilon_{ijt} \sim N(0, \sigma_\epsilon^2)$ represents random error that changes across t and i .

X_{ijt} constitutes control variables which are demographic, socio-economic and clinical confounders (age, sex, caregiver marital status, work status, ADL function), and stratification variables used in the design stage.

Due to the non-normal distribution of hours and costs we will use both linear mixed-effects, as well as general lineal mixed regression model for assessing both primary variables. For RSS, and other continuous variables, we use Linear Mixed regression model. Log-transformation of the outcome will also be considered to address potential non-normality in the response.

Intervention effect

In secondary analysis, we will further examine the extent to which the treatment effect will depend on the calendar time when COVID lockdown happened, and the potential for delayed effect. We collectively refer these effects as heterogeneous treatment effect, and provide a schematic illustration following Section 3.2 of Li et al. (2020) [6]. The rationale is that there the lockdown during the pandemic may contribute to change in the intervention effect. In addition, the intervention may be most effective when it is first introduced, and the sustained effect may be smaller. Therefore, when modelling the intervention effect, we will allow for heterogeneous effect and assess the robustness of our primary analysis. The table below shows how the intervention effect can differ between periods (t) across different groups (g). The deltas (δ) constitute the intervention effect, and their subscript defines heterogeneous effects where δ_0 is the pre-lockdown intervention effect, δ_0^* is the intervention effect post-lockdown, and δ_1^* is the follow-up post-lockdown treatment effect.

When modelling the intervention effect, we will test the null-hypothesis (H_0)

$$\delta_0 = \delta_0^* = \delta_1^*$$

	$t = 1$	$t = 2$	$t = 3$	$t = 4$
$g = 3$			δ_0^*	δ_1^*
$g = 2$		δ_0^*	δ_1^*	δ_1^*
$g = 1$	δ_0	δ_1^*	δ_1^*	δ_1^*

Economic evaluation

If we identify an average treatment effect on one of the primary and secondary outcomes, we will use cost-efficiency (CEA) and cost-utility analysis (CUA) to evaluate the economic effects of the LIVE treatment.

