The definition of treatment assignment as specified in section “Analysis sets” will be used in this section, too.

Deviations from the randomized treatment sequence occurred under the first Covid-19 lockdown, see section Modification History, Changes to the study protocol

Treatment duration

Each municipal coordinators are writing logs, and we will collect the data and calculate total hours of care by the coordinator, divided into different categories.

Descriptive statistics for the total hours of care by the coordinators will be presented.

Delivery of the intervention

One coordinator from the municipal per dyad

Efficacy

Primary efficacy analysis

The primary efficacy analysis variable caregiver burden is based on two variables. The first is RUD, divided in three categories: number of hours the last 30 days invested in personal, instrumental and supervisory care. The second is RSS measured as total score but also

specific and clustered items. Lower hours of informal care as well as lower score of RSS, indicates reduction in caregiver burden.

The null hypothesis states that there are no differences in burden and resource utilization between the LIVE intervention and usual care. The primary alternative hypothesis (H1) states that the LIVE intervention will improve caregiver burden and resource utilization compared with usual care. The secondary alternative hypothesis (H2) is that the LIVE intervention will provide more cost-efficient services than usual care.

H0: LIVE treatment = control

H1: LIVE treatment > control

H2: cost efficiency > control

where LIVE treatment denotes the proportion of caregivers experiencing improvement in care burden. The primary hypothesis will be statistically assessed by means of a χ^2 test on the one-sided significance level of 2.5% (corresponding to 5% two-sided).

We will plot the regression line to visualize the parallel effect for both treatment group and control group.

The significance level will be set to 2.5% (one-sided, corresponding to 5% two-sided), the corresponding level of one-sided CI is 97.5% (corresponding to 95% two-sided).

Missing data

We will pre-specify a list of baseline covariates that are likely associated with the missingness and the outcome, and adjust for these covariates in our primary analyses. This covariate-adjusted analysis will be valid under the missing at random (MAR) mechanism.

Sensitivity and robustness tests of regression analyses and economic evaluation

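### The SAP promises the economic evaluation as part of the primary endpoint, but runs it only if an effect is identified on one of the primary and secondary outcomes

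*SAP*

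**What the plan says.** **Without condition.** In the Study Design table, the primary objective states that "we will evaluate the economic consequences of the treatment by calculating Incremental Cost-Effectiveness Ratio (ICER) and quality adjusted life years (QALY"). The Endpoints row of the same table places "Change in Cost-efficiency of treatment" under the primary endpoint. The Economic evaluation section has costs and QALYs measured in every six-month phase. The section on sensitivity and robustness tests plans a simulation over cost levels and plots of the ICER. Under Primary efficacy analysis, a hypothesis is stated: "The secondary alternative hypothesis (H2) is that the LIVE intervention will provide more cost-efficient services than usual care".

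**With condition.** The Economic evaluation section opens with: "If we identify an average treatment effect on one of the primary and secondary outcomes, we will use cost-efficiency (CEA) and cost-utility analysis (CUA").

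**What bears on the condition.** The Causal model section defines the average treatment effect as the coefficient β1 in model (1). General statistical methods says: "Unless otherwise specified, all statistical tests will be two-sided". Primary efficacy analysis tests the primary hypothesis with a chi-square test "on the one-sided significance level of 2.5% (corresponding to 5% two-sided"), and later repeats that level without naming a test.

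**The concern.** The two sets of statements cannot both be followed when no effect is identified. The endpoint list then calls for a cost-efficiency result and the Economic evaluation section does not produce one. The SAP does not say what is reported in that case.

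The condition also works against the question asked. The cost-efficiency hypothesis could be true because the intervention costs less at a similar effect, and in that situation the condition may well not be met. An economic evaluation estimates a difference in costs and a difference in effects together with their uncertainty, and neither has to be significant first.

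At stake is whether the cost-effectiveness and cost-utility analyses appear at all. As planned, that depends on the results for other outcomes and on a criterion that the SAP leaves open.

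**Working it through.** **1. The passages side by side.**

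| Place in the SAP | Economic result | Condition |
|---|---|---|
| Study Design, primary objective | ICER and QALYs calculated | none |
| Study Design, Endpoints | cost-efficiency under primary endpoint | none |
| Economic evaluation, opening | CEA and CUA | effect on one of the primary and secondary outcomes |
| Economic evaluation, later text | costs and QALYs per six-month phase | none |
| Primary efficacy analysis | H2, called secondary | none |
| Sensitivity and robustness tests | simulation, ICER plots | none |

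Read literally, the condition is partly circular, because cost-efficiency is itself listed as primary. The workable reading, used here, is that the clinical and burden outcomes open the gate.

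**2. What the gate leaves open.** The estimand is named (β1) and a level exists. What is missing is a link from either to the gate, the direction of effect that counts, the set of outcomes that count, and a multiplicity rule.

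**3. How often chance alone would open it.** The SAP gives no figure for this, so there is none to reproduce. Assumptions: to identify an effect means an unadjusted significant result; no outcome has a true effect; the test statistics are normal with a common correlation ρ.

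The number of eligible outcomes k depends on the reading:
- k = 4: the primary burden measures. For RUD, "we will use all three subcategories of RUD separately", which gives three, plus the RSS total.
- k = 8: these four plus EQ-5D-5L, EQ-5D-VAS, QoL-AD and NPI, following the Secondary efficacy analyses section, which names only quality of life and NPI.
- k = 13: these eight plus CMAI, GDS, ADL, IADL and CGIC, following the secondary objectives.

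For independent outcomes, P(open) = 1 − (1 − α)^k:
- two-sided 5%, k = 13: 1 − 0.95^13 = 0.487; k = 4: 1 − 0.95^4 = 0.185
- one-sided 2.5%, k = 13: 1 − 0.975^13 = 0.280; k = 4: 1 − 0.975^4 = 0.096

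For correlated outcomes, P(open) = 1 − ∫ [P(no rejection | u)]^k φ(u) du, where u is the shared normal component.

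| k | Test | ρ = 0 | ρ = 0.3 | ρ = 0.5 | ρ = 0.7 |
|---|---|---|---|---|---|
| 4 | two-sided 5% | 0.185 | 0.174 | 0.156 | 0.130 |
| 8 | two-sided 5% | 0.337 | 0.300 | 0.250 | 0.191 |
| 13 | two-sided 5% | 0.487 | 0.418 | 0.334 | 0.241 |
| 4 | one-sided 2.5% | 0.096 | 0.087 | 0.078 | 0.065 |
| 8 | one-sided 2.5% | 0.183 | 0.152 | 0.125 | 0.095 |
| 13 | one-sided 2.5% | 0.280 | 0.214 | 0.167 | 0.120 |

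The range is 13% to 49% two-sided and 6.5% to 28% one-sided. Counting quality of life separately for the person with dementia and the caregiver would raise k further.

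**4. If the design effect is real.** Sample size estimation plans 80% power for a 7 h/week difference with SD 20. The usual two-group formula gives 2 × (1.960 + 0.842)² × 20² / 7² = 128.2, so 129 per group and 258 in total, against the stated 260. If that power carried over to one gate outcome, the evaluation would be skipped in at most 1 − 0.80 = 20% of trials.

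**5. Selection.** The Economic evaluation section uses RUD, RSS, quality of life, NPI and function as effect measures. Where one of these opened the gate by reaching significance, its estimate, taken over the trials that pass, is exaggerated away from zero. The size depends on the unstated rule, so none is given.

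**The case against.** The strongest reply is that a specific methods section may qualify a summary table, so that the condition refines the earlier promise. Calling H2 a secondary alternative hypothesis also fits with testing it after H1. The second part stands: H2 alone does not establish the conflict. The first does not remove it, because the SAP nowhere says that the endpoint is conditional or what is reported if the condition fails.

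Several stronger readings are tempting, and the SAP does not support them:
- *That the gate has no basis for a decision.* β1 is defined and a general level is stated. The gap is the missing link, direction, outcome set and multiplicity rule.
- *That there are two competing significance levels.* The SAP equates 2.5% one-sided with 5% two-sided. The difference between the two halves of the table reflects only whether significant worsening also opens the gate.
- *That 13 outcomes is a given.* It is one reading; another section supports about 8.
- *That skipping the evaluation is the typical result.* The probabilities above describe a trial with no effect on any outcome.
- *That selection biases the effect upward.* If harm can open the gate, the exaggeration can go either way. The section also relates costs to all the listed outcomes, not only the one that opened the gate.
- *That no economic result would appear.* The Causal model section says "Due to the non-normal distribution of hours and costs we will use both linear mixed-effects" and generalised models, without a gate, so a plain cost comparison may still be reported. The CEA and CUA are what is at risk.

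**Conclusion.** The contradiction holds on the SAP's own text: a result listed under the primary endpoint and promised without condition is elsewhere made to depend on other results. This needs no calculation and rests only on reading the gate as the clinical and burden outcomes. The opening probabilities in the working illustrate how loosely the gate is set under a global null with unadjusted tests; they do not forecast this trial. The change should be made, because the reporting of a primary-endpoint component depends on it. The analyses of caregiver burden are not affected.

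**What to change.** 1. In Economic evaluation, replace the condition with a sentence such as: *CEA and CUA will be performed regardless of the clinical results.*
2. Report incremental costs and incremental effects separately, with their joint uncertainty, as a distribution on the cost-effectiveness plane. The sensitivity section currently offers a ratio or a distribution; the ratio alone is unstable when the effect is near zero.
3. State once whether cost-efficiency is primary (Study Design, Endpoints) or secondary (H2, Primary efficacy analysis), and align the other places.

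Defining the gate more precisely would remove the ambiguity but leave reporting dependent on results.

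The cost is SAP wording and some analysis work; costs and QALYs are to be measured in each phase anyway. The downside is that an economic result must be reported even when the clinical effects are null.

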In cost-effectiveness analysis the effect is measured in health units (or other outcome measures depending on the context). The outcomes are common health measures in natural units, and the results are presented as cost per effect unit/outcome measure. In cost-utility analysis, also called cost per QALY analysis, the effect is measured as quality-adjusted life years (QALYs) on a scale of 0 (death) and 1 (full health). A quality-adjusted life year (QALY) captures both life years gained and improved health as a result of treatment [8, 9].

The economic evaluation will be measured at society level.

Costs and QALYs will be measured for each phase of 6 months

The cost-effective analysis will relate the difference in total mean costs at societal level per 6 months between all intervention -and usual care phases to the difference in RUD, RSS, QoLs, QALYs, NPI, function level such as ADL and IADL

The analysis will use a discounting rate at 3.5%.

Following other costs studies calculating RUD in an advanced economy setting, our analysis will use 35% of the Norwegian average income to value lost leisure time for retired caregiver.

The primary economic evaluation will use the opportunity cost method to assess the costs of informal caregiving. For a sensitivity analysis, the replacement cost will be used.

Unit costs will be based on information from Statistics Norway and information from the primary health care institutions in each municipalities.

Covariates and strata

In the main statistical analyses, the following covariates are used for both caregivers and PwD.

For PwD: Age, sex, marital status, cohabitation status, number of co-caregivers, clinical characteristics of dementia (dementia etiology, neuropsychiatric symptoms, functional level)

For Caregivers: Age, sex, marital status, cohabitation status, numbers of co-caregivers involved in caregiving for the PwD, work status, use of health care services,

Groups, municipalities

Municipalities will be grouped in the main analysis and used as an adjustment variable (fixed effects). This is not the case for district municipalities as we consider that the dyads are similar within municipalities

Subgroups

In subgroup analyses, the following covariates will be used to define relevant subgroups:

- Gender (male, female)
- Work (retired and working caregivers)
- Caregiver relation (spouse, children)
- Residency (living alone, or with caregiver)

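### The cost per RUD hour counts informal care on both sides of the ratio, and no time-adjusted estimator is named for the cost and QALY differences

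*SAP*

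**What the plan says.** **Costs.** Under Economic evaluation the SAP sets the perspective ("The economic evaluation will be measured at society level") and the valuation ("The primary economic evaluation will use the opportunity cost method to assess the costs of informal caregiving"), with replacement cost as a sensitivity analysis. One group has its own value: "our analysis will use 35% of the Norwegian average income to value lost leisure time for retired caregiver". The income figure itself is not given.

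**Ratio.** The numerator is a contrast of mean total societal cost in each half-year, which the plan sets out as the one "between all intervention -and usual care phases to the difference in RUD, RSS, QoLs, QALYs, NPI"; measures of function complete the list of effects.

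**Effect unit.** Primary efficacy analysis defines RUD as "number of hours the last 30 days invested in personal, instrumental and supervisory care". Both that section and Study Design treat the three categories separately.

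**Time.** The Causal model section says that "time related confounders are important to adjust for [5] when assessing treatment effect". Model (1) contains an intercept, a treatment indicator, covariates, a participant random effect and error. The covariates listed for it are age, sex, caregiver marital status, work status, ADL function and the stratification variables. The fuller list under Covariates and strata has no period or calendar-time term either. The text after model (1) mentions mixed models for hours and costs because of non-normality. The Economic evaluation section names no model for the cost or QALY difference.

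**The concern.** A cost-effectiveness ratio should set the net cost of an intervention against an effect that has not already been turned into money. Here informal-care hours saved are priced and subtracted from cost, and the result is then divided by those same hours. A reader of the cost per hour of care avoided would take it as the price of relieving caregivers. In fact it is that price less whatever hourly value the analyst assumed.

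The second issue is time. In a stepped-wedge trial usual care comes early and intervention comes late. If care needs grow, or services change in the pandemic, a cost or QALY difference that is not adjusted for period absorbs that change. This would reach every ratio, including cost per QALY. The economic evaluation is not peripheral: ICER and QALY stand in the primary objective, cost-efficiency in the primary endpoint, and H2 is a cost-efficiency hypothesis.

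**Working it through.** **1. The plan's own figure.** The SAP gives no number for the economic evaluation. The nearest is the sample size: difference 7 h/week, SD 20, 80% power, 5% two-sided. Per arm n = 2 × (1.960 + 0.842)² × 20² / 7² = 128.2, rounded up to 129, or 258 dyads against 260 stated. It reproduces to within rounding, so I use 7 h/week as the effect size.

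**2. Double counting.** Let C be the difference in all societal costs other than informal care (intervention minus usual care, per six months), h the total costed hours saved, and w the average value of a saved hour.

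- Numerator: C − w·h.
- Ratio per hour saved: (C − w·h)/h = C/h − w.
- If one RUD category with saving h₁ is the denominator: C/h₁ − w·(h₁ + h₂ + h₃)/h₁. With equal savings in the three categories the shift is 3w.

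Take 7 h/week × 26 weeks = 182 hours and, as assumptions, C = 20,000 or 50,000 and w = 100 to 300 currency units:

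| w | Ratio, C = 20,000 | Ratio, C = 50,000 |
|---|---|---|
| informal care not costed | 20,000/182 = 110 | 50,000/182 = 275 |
| 100 | 1,800/182 = 10 | 31,800/182 = 175 |
| 200 | −16,400/182 = −90 | 13,600/182 = 75 |
| 300 | −34,600/182 = −190 | −4,600/182 = −25 |

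The sign changes at w = C/h. Replacing opportunity cost by replacement cost changes w and leaves the overlap in place. So does the planned simulation of cost levels.

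**3. Position of the phases in time.** In the grid under Intervention effect (t = 1 to 4, six months each) the intervention and follow-up cells are {1, 2, 3, 4}, {2, 3, 4} and {3, 4}: mean 26/9 = 2.89. The usual-care cells are {1} and {1, 2}: mean 4/3 = 1.33. Other definitions follow in the same way. The last three columns give the drift added to an unadjusted contrast by an assumed rise in care hours per six months.

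| Intervention cells | Baseline as usual care | Gap, periods | Gap, months | Rise of 1 h/week | Rise of 2 h/week | Rise of 4 h/week |
|---|---|---|---|---|---|---|
| all | no | 1.56 | 9.3 | 1.6 | 3.1 | 6.2 |
| active only | no | 0.67 | 4.0 | 0.7 | 1.3 | 2.7 |
| all | yes | 2.22 | 13.3 | 2.2 | 4.4 | 8.9 |
| active only | yes | 1.33 | 8.0 | 1.3 | 2.7 | 5.3 |

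A drift of 3.1 h/week is 3.11 × 26 = 80.9 hours per six months. At 100 to 300 per hour that puts about 8,100 to 24,300 into the numerator of every societal ratio. On the planned dates 1 of 9 intervention cells precedes the lockdown, against 2 of 3 usual-care cells.

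**4. Would the mixed model cure it?** Forty simulated trials were run at each of two within-dyad correlations: 3 sequences of 105 dyads, baseline plus four assessments, SD 20, true effect −7 h/week, assumed rise 2 h/week per six months, no covariates. Mean estimates:

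| Estimator | Correlation 0.1075 | Correlation 0.5 |
|---|---|---|
| difference in phase means | −2.5 | −2.6 |
| model (1), no period term | −2.3 | −2.1 |
| model (1) plus period effects | −7.2 | −7.2 |

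The Monte Carlo standard errors are 0.14 to 0.21. Without a period term the mixed model does no better than the difference in means.

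**The case against.** The best reply concerns the time point. A reader might infer that the plan compares raw phase means. The text does not support that: it says what is compared, not how the difference is estimated, and the SAP elsewhere mentions mixed models for hours and costs. It also says that time matters. What stands is narrower: no time-adjusted estimator is written down, and the one model given has no period term. The heterogeneity analysis under Intervention effect does not fill the gap. It is secondary, and it lets the treatment effect vary with lockdown and follow-up, which is not a period main effect. Some covariates, such as ADL function if updated at each assessment, might absorb part of a trend, but none is a period term.

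On the double counting, three stronger readings fail.

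- The ratio does not reflect only the hourly value and calendar time, because C/h remains in it.
- The shift is not always exactly w. That holds for total costed hours at one average value, while the SAP splits RUD into three categories and values retired caregivers separately.
- The overlap does not extend to the ratios per RSS, QoL, QALY, NPI or function unit. The hourly value enters their numerators too, and can change their sign, but their denominators are not the priced hours.

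It is also fair that a gap of 9.3 months is an imbalance and not a bias. It becomes one only with a time trend, for which the SAP gives no figure. The gap rests on the nominal schedule, and Modification History records that the intervention was postponed in two municipalities.

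**Conclusion.** The point holds in two parts of different strength.

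The overlap in the RUD ratio follows directly from the text and is certain. One unit of assumed hourly value moves the ratio by one unit for total hours, and by more if a single category is the denominator. The illustrative amounts rest on assumed other costs and hourly values; the dependence does not. Nothing in the SAP removes it.

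The time part is an omission in specification: the SAP calls for adjustment but does not provide it for costs or QALYs. With an assumed rise of 2 h/week per six months, the unadjusted contrast on the nominal grid is off by 1.3 to 4.4 h/week against a target of 7, depending on which cells count. The bias in costs and QALYs cannot be given, because the SAP states neither unit costs nor trends. Both parts should be corrected before analysis.

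**What to change.** 1. Either remove RUD hours from the effect units for societal ratios and report them as an outcome in natural units, or keep the RUD ratio and exclude informal-care cost from its numerator, so that it becomes C/h. If it is kept, state whether the denominator is total hours or one category, and put RUD (30 days) and costs (six months) on the same time base.
2. Estimate the cost and QALY differences from a mixed model with a dyad random effect and explicit period fixed effects. Do not simply refer to model (1), which lacks the period term as written.
3. State whether follow-up phases count as intervention and whether baseline counts as usual care.

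This changes SAP wording only and needs no new data. The price is precision: in the simulation, adding period effects raised the Monte Carlo standard error, and so the spread of the estimate, by a factor of roughly 1.2 (0.180/0.146) to 1.5 (0.209/0.137), so intervals will be somewhat wider.
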